management software tool.⁷¹ Team members will meet regularly to review the coding strategies and themes that emerge from further analysis of the thematic and categorical reports that will be generated following coding. We will continue analysis until no new major themes emerge. We will address recognized criteria for qualitative research: credibility, fittingness, auditability, and confirmability.⁷²

(5) HUMAN SUBJECTS

The overall goal of this project is to evaluate the Secure Messaging for Medication Reconciliation Tool (SMMRT) for the purposes of post-discharge medication reconciliation. This project proposes two types of research: Aim 1 is quantitative: an RCT to compare the effect of an intervention on the medication reconciliation process following discharge from the hospital. Aim 2 is qualitative, gathering the preferences, attitudes, and behaviors of Veterans and VA pharmacists and nurses regarding the SMMRT tool and its implementation.

Aim 1: Risk to Subjects

Human Subjects Involvement and Characteristics

The goal of Aim 1 is to conduct a two-arm RCT to evaluate the effects of SMMRT. This trial will compare 1) Usual Care (UC) with 2) UC plus pharmacist-mediated medication reconciliation via SM using SMMRT among Veterans discharged from the hospital. A total of 240 Veterans will be recruited for Aim 1 once deemed appropriate for the study. The study will be explained to Veterans who express interest, and informed consent will be obtained. Veterans will be informed that their care will not be affected if they choose not to participate in the study. Next, Veterans will be randomized to condition, and the baseline interview will be administered. If the Veteran is randomized to UC plus SMMRT, the research associate will instruct the Veteran on how the tool works. When the Veteran has completed the training with the SMMRT tool, the research associate will ensure no other questions remain. Veterans in the UC plus SMMRT Intervention condition will be monitored during the length of the study. A total of 20 Veterans from the experimental arm of Aim 1 will be contacted for a post- intervention in-depth interview (See Aim 2 below).

Sources of Materials

Data to assess the outcomes of the RCT will be derived from review of the medical record (CPRS and VistAWeb), the *Corporate Data Warehouse (CDW)*, and telephone-based interviews with participants.

Potential Risks

The risks to subjects from our study are minimal. The primary risk to Veterans is disclosure of sensitive information. In general, as in virtually any human research study, there is a risk of data security breach and resulting loss of confidential study data. Our procedures are designed to prevent any unauthorized disclosure; see Adequacy of Protection from Risk, below. We do not anticipate any adverse effects of the research to require any medical or professional intervention.

Adequacy of Protection from Risk

Recruitment and Informed Consent

All research staff will be trained on protection of human subjects, and regularly supervised to ensure respect for potential participants, integrity of data collection, and appropriate interactions with staff. Veterans will be informed that their participation in the study is voluntary, and refusal to participate will not change the care they receive.

Protection against Risk

As described above, the potential risks to Veterans in Aim 1 are minimal. The main risk is loss of confidentiality of sensitive information. Recruitment will take place on inpatient units within VA Boston, as will the consent process, baseline interview and SMMRT tool training. If randomized to the SMMRT intervention,

all medication data will remain in My HealtheVet, never leaving the VA firewall. When conducting the follow-up telephone interviews, the *research associates* will confirm that they are speaking with the proper Veteran participant. The *research associate* will only leave telephone messages saying that the Veteran is participating in a health study.

We will only collect identifiable data when absolutely necessary and scientifically justified. The SMMRT will be sent through the secure messaging feature of My HealtheVet. Only the Veteran and study pharmacist will have access to the medication data. Data transmissions between study staff will be minimized, but when necessary, will meet or exceed all standards for encryption and security that are in place for the electronic transmission of Veterans' clinical information, with which the Principal Investigator is familiar.

Aims 2: Risk to Subjects

Human Subject Involvement and Characteristics

Aim 2 will involve telephone interviews with 20 Veterans who were allocated to the experimental arm of the RCT, with the use of semi-structured, in-depth interviewing techniques to assess Veterans' experience with the SMMRT tool. *In addition, Aim 2 will include brief, focused interviews with 10-15 PACT nurses and 5-10 PACT pharmacists from VISN 1 facilities regarding their perceptions of whether and how the SMMRT intervention may have affected their post-discharge follow-up calls. The interviews with nurses and pharmacists will also explore unanticipated consequences of the SMMRT intervention.*

Sources of Materials

During the course of conducting study Aim 2, we will collect data through interviews with Veterans, VA pharmacists, and nurses. Thus, all of the research material for this study will be data obtained specifically for research purposes.

Potential Risks

This study involves a low level of risk to all human subjects. There are no apparent physical risks for any of the subjects. In general, as in virtually any research study, there is a risk of data security breach and resulting loss of confidential study data. There is potential risk that the questions and conversations in the interviews could be psychologically upsetting to the Veterans. There is also the theoretical possibility that participating in the interviews could be physically taxing. Additionally, VA staff members are considered a vulnerable group, due protections exceeding their Veteran counterparts. The likelihood of any of these risks is low. None of these potential risks is serious.

Adequacy of Protection from Risk

Recruitment and Informed Consent

Veterans: For Aim 2, we will identify Veterans allocated to the experimental condition (Usual Care + SMMRT Intervention) at the time of the 30-day follow-up telephone call. These Veterans will already have provided informed consent at the time of their enrollment in Aim 1. However, they will be reminded of the key elements of informed consent at the time of invitation to participate in Aim 2. Veteran participants will be informed that the collection of data will be strictly confidential and that the participation of all human subjects will be completely voluntary. The "script" that research staff will use in approaching Veterans for recruitment in the interviews will explicitly indicate the voluntary nature of participation and the assurance of confidentiality of respondents.

VA Pharmacists and Nurses: A member of the study team will reach out to potential staff participants for Aim 2, as described in the Protocol. Those interested in participating will be educated on the study, made aware that participation will not impact employment status, and be provided a forum to address questions and

concerns. VA employee participants will be informed that their data collection from *interviews* will be strictly confidential and their participation will be strictly voluntary. Please refer to the e-mail and telephone script submitted separately, which explicitly indicate the voluntary nature of participation and the assurance of confidentiality of respondents, as well as special rights and protections afforded for VA staff participating as research subjects.

Protection against Risk

As described above, the potential risks to subjects in this study are of low likelihood and generally not serious. Nevertheless, we have given these risks careful consideration and have developed a plan to ensure that research subjects are protected against them. With respect to ensuring confidentiality and data security, we will take the following precautions. We will only collect identifiable data when absolutely necessary and scientifically justified. Data will only be stored on VA servers, never leaving the VA system. We note that our servers for data storage are located on a separate research-specific password-protected server, providing an additional layer of security. Data transmissions between study staff will be minimized, but when necessary, will meet or exceed all standards for encryption and security that are in place for the electronic transmission of Veterans' clinical information, with which the Principal Investigator is familiar. Recordings of participants during laboratory observations and in-depth interviews will be treated with similar care. The audio recordings will be made with a portable digital recording device that will always be maintained under lock-and-key of study staff (either in locked file cabinets within a locked office, or, when in transport between facilities, within a locked box). The digital recordings will be downloaded to password-protected computer files on the VA network server (behind the research firewall), and transcriptions from these recordings will be similarly stored and handled. Prior to processing the transcriptions for qualitative analysis, study staff will remove all names and other personal identifiers from the transcripts. *Transcripts will not be printed routinely. Rather, study team members will be instructed to review them as electronic files, to minimize the risk of PHI disclosure.*

We expect these processes, which our team members have employed in a variety of studies both within and outside the VA, will be highly effective in protecting subjects from the risks of data security and confidentiality breaches. With respect to protecting participants from the risk of psychological distress and physical taxation as a result of participating in the interviews, we will take the following precautions. First, we will ensure that VA facilities be accessible to all participants, with special attention to needs of those with physical disabilities. Second, we will train the research associate to be sensitive to any discomfort that the subject may be experiencing; [name] has extensive clinical and research experience related to interviewing and will ensure that the research associates have sufficient training in this regard. Third, we will ensure that sufficient research staff members are present to assist participants in locating restrooms and other necessary facilities.

We do not anticipate any adverse effects of the research to require any medical or professional intervention.

Aims 1 and 2: Potential benefits of research to subjects and others

This application proposes to develop a secure messaging medication reconciliation tool Intervention to improve the post-discharge medication reconciliation process, and compare its effectiveness with treatment as

usual. The potential benefits of this research to Veterans include greater accuracy in the post-discharge medication reconciliation process, resulting in improved health of Veterans. We also anticipate that this intervention, if proven effective and, ultimately, integrated successfully into the post-discharge medication reconciliation process, will lead to reduced medication errors, fewer hospitalizations and adverse drug events. Finally, this line of research can lead to the demonstration of the utility of an eHealth tool that Veterans with less comfort with technology can use, leading the way toward additional behavioral interventions that do not add to the clinic's workload. We believe that these benefits do outweigh the minimal risk of harm to research subjects, thus justifying the research.

Importance of knowledge to be gained

This project is unique in that it brings together three high priority areas for VA; improving medication reconciliation interventions, specifically, secure message based medication reconciliation tools; transforming care through the use of healthcare informatics, specifically, the SMMRT tool; and reducing racial and ethnic minority health care disparities, through the use of an eHealth tool that has few barriers to use by Veterans who may have poor health and computer literacy. If ultimately proven effective, the use of this eHealth tool for multiple behavioral issues can be integrated into the interface between primary care and behavioral health, and can fit well into the model of Patient Aligned Care Teams.

The knowledge to be gained from this study will be significant in addressing three high priority areas at once, and point to the pathway for using patient-facing technology to meet the 21st century requirements for all of our Veterans to be more involved in their own care. It will provide information on integrating eHealth tools into primary care as well as the effectiveness of this tool, at least for medication reconciliation. The potential knowledge to be gained from this project outweighs the minimal risks to participants.

Data and Safety Monitoring Plan

[name], as principal investigator, and the VA Boston IRB will be responsible for monitoring the safety of participants. The Data and Safety Monitoring Plan will be carried out by [name]. Research staff will be trained to understand and document adverse and serious adverse events, and to immediately call [name] in the case of such an event. [name] will immediately notify the IRB of the adverse event and appropriate clinical action will be taken. A Case Report Form will be created that will be used to report all adverse events. This form will include the participant's study number and all relevant information about the adverse event. Case Report Forms will be filled out immediately by the staff person who is responding to the problem. Serious adverse events will be reported to the VA Boston IRB within 48 hours of its occurrence. All other adverse events will be reported annually to the IRB and HSR&D.

Inclusion of women, minorities and/or children

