The setting of Aim 1 will include not only the acute inpatient hospital (located on the West Roxbury Division Campus) but also the CLC, located on the Brockton Division Campus.

2. Recruitment and enrollment

Approximately ten (10) patients per week are discharged to home from the CLC each week. Because of the strong relationships developed between the clinical teams and the Veterans and their families during the long (compared with acute inpatient) hospitalizations, typically 3-4 weeks, Veterans are likely to be amenable to enrolling in a clinical research trial that they see their clinical team members advocating. Conservatively, we estimate that at least 2 patients each week will enroll in SMMRT, such that over the course of 12 months (50 weeks), a minimum of 100 patients would be enrolled. In addition, we have ensured that resources are available to enroll 140 patients at the West Roxbury setting, resulting in a total sample size of 240 subjects. Recruitment and enrollment processes will follow these steps:

1. Research staff will communicate regularly with clinical staff (nurses and clinicians) on the inpatient service at VA Boston's West Roxbury and Brockton Divisions
2. Research staff will identify any Veterans hospitalized on the Inpatient Service meeting the following criteria by reviewing CPRS, patient lists, and consulting with clinical staff:
 - a. age 18 years or older
 - b. having a VA primary care provider (PCP) at any VA facility in VISN-1
 - c. planned discharge home (as opposed to another facility)
 - d. anticipated to be discharged with at least 5 medications
3. Research staff will confirm with clinical staff that the Veteran/patient may be approached and informed about the study.
4. Research staff will approach the hospitalized Veteran to describe the study and seek informed consent for participation.
5. The research staff will briefly describe the study and then administer the Callahan cognition screener (see separate document) and the eligibility screening questions below.
6. If the Veteran passes the Callahan cognition screener and eligibility screening questions, the research staff member will seek to obtain informed consent and HIPAA Authorization.

Script for Aim 2 Eligibility Screening Questions (after Callahan Screening and before Informed Consent):

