- Thank you for allowing me the chance to tell you about our study. I would like to ask you a few questions first to see if you meet the requirements for eligibility. Would that be okay?

[figure not shown]
1. **Do you have access to a computer? Y/N** (*If yes, continue. If no skip to question 4*)
2. **Do you use a computer to connect to the internet, say to search websites or for email?**
3. ***If yes, Do you use secure messaging? If no, would you be willing to use it if required for this study?***
4. **Does anyone help you manage your medicines? Y/ N** (*If yes, continue. If no, not eligible, go to Verbal consent*)
5. **Does that person use a computer/ internet/ email? Y/N** (*If yes, continue. If no, not eligible, *Would you be willing to have your caregiver use secure messaging on your behalf if required for this study?**

If no to either 2 or 3: Unfortunately, you do not meet the criteria to participate in this study. Thank you for your time and interest.

→If Yes to 3 and 4, administer the Callahan screener. If patient passes the screener, then the patient is eligible. Continue on to ICF and HIPAA forms.

3. Randomization and intervention

Veterans successfully recruited and consented to participate will be randomly allocated to either UC or UC+SMMRT. Veterans randomized to UC+SMMRT will receive introduction to My HealtheVet and SMMRT. Within 3 business days of discharge, the SMMRT Research Pharmacist will engage with Veterans and/or their designated family members to conduct medication review and reconciliation via Secure Messaging. See randomization scheme below.

After baseline assessment is complete, participants will be randomly assigned via computer program to receive 1) usual care or 2) UC plus pharmacist-mediated medication reconciliation (SMMRT). After opening, the research assistant will inform the Veteran of the “treatment assignment.”

Overview of the Intervention

[figure not shown]
The intervention principally entails the creation of a personalized medication list for each Veteran/subject, incorporating most current data from Vista (the medical record) into a user-friendly PDF-file interface, i.e. the SMMRT. The research pharmacist will send the SMMRT via attachment to Secure Message to the Veteran and will then interact with the Veteran to ensure that the medical record accurately reflects what medications the Veteran is taking.

What Happens in the Intervention?

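### The eligibility script contradicts itself: read literally, it admits only Veterans who answer yes to all five questions, or nobody, although the inclusion criteria require no medication helper

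*Combined protocol and SAP*

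**What the plan says.** The script is in the combined protocol and SAP, Section (4) Work Proposed, Methods for Aim 1, item 2 (Recruitment and enrollment). Under step 6 of that item, consent is sought only from Veterans who pass both the cognition screener and these questions.

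The routing is as follows.

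- **Question 1** (computer access): "If no skip to question 4".
- **Questions 2 and 3** (internet use; use of Secure Messaging or willingness to use it): no routing note of their own.
- **Question 4**: "Does anyone help you manage your medicines? Y/ N". The note for a negative answer is "If no, not eligible, go to Verbal consent".
- **Question 5** (whether the helper is online): a no is also marked ineligible. The same item asks "Would you be willing to have your caregiver use secure messaging on your behalf if required for this study".
- **Closing rejection rule**: "If no to either 2 or 3: Unfortunately, you do not meet the criteria to participate in this study".
- **Closing acceptance rule**: "If Yes to 3 and 4, administer the Callahan screener. If patient passes the screener, then the patient is eligible".

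Inclusion criteria a to d, in step 2 of the same item, cover age, a VA primary care provider in VISN-1, planned discharge home, and being "anticipated to be discharged with at least 5 medications". None mentions a helper. Item 3 (Randomization and intervention) says that "the SMMRT Research Pharmacist will engage with Veterans and/or their designated family members to conduct medication review and reconciliation via Secure Messaging".

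**The concern.** Item 3 describes two ways of taking part: the Veteran uses Secure Messaging, or a family member does so for the Veteran. The script seems to have been built for the same two routes, since question 1 diverts Veterans without a computer to the helper questions. But the acceptance rule joins the routes with an *and*, and the notes at questions 4 and 5 reject Veterans who never needed a helper.

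This matters because the script is the operative gate to consent and randomisation. If staff follow it literally, the trial enrols a narrower group than the intervention text describes. If staff work around it, eligibility depends on who is screening, at two campuses, and the protocol holds no correct rule against which to audit their decisions.

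**Working it through.** No figure in the plan is in dispute. The enrolment target reproduces (2 per week × 50 weeks + 140 = 240), and the power statement does not depend on this point. The check is one of logic: take each type of Veteran through the written notes and the two closing rules.

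The text does not say whether a Veteran who answers yes to questions 1 to 3 goes on to question 4, so both readings are needed.

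- **Reading A:** the questions are asked in order, and only a no to question 1 causes a skip.
- **Reading B:** questions 4 and 5 are asked only after a no to question 1.

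Here *online* means yes to questions 1, 2 and 3, where yes to 3 covers both current use and willingness.

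| Veteran | Reading A | Reading B |
|---|---|---|
| Online, with an online helper | Eligible | No rule admits (question 4 not asked) |
| Online, manages own medicines | Rejected at question 4 | No rule admits |
| Online, helper offline | Rejected at question 5 | No rule admits |
| Has a computer, no to 2 or 3, online helper | Rejected by closing rule | Rejected by closing rule |
| No computer, online helper | No rule admits | No rule admits |
| No computer, no helper or helper offline | Rejected at 4 or 5 | Rejected at 4 or 5 |

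Four things follow.

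1. Under reading A the only route to eligibility is yes to all five questions. Under reading B nobody answers both 3 and 4, so nobody qualifies.
2. The online self-manager is admitted under neither reading. Dropping the note at question 4 does not help, because the acceptance rule itself needs a yes to 4. Yet this Veteran can meet all of criteria a to d, and can carry out the steps that the intervention section assigns to the Veteran: receive, download, correct and return the list.
3. The online Veteran with an offline helper meets the acceptance rule (yes to 3 and 4) and is marked ineligible at question 5. Under reading A the two instructions conflict directly.
4. The Veteran without a computer never answers 2 or 3. The rejection rule, which needs a no to one of them, does not apply, and the acceptance rule, which needs a yes to 3, cannot be met. This Veteran is left unclassified. A Veteran who has a computer but answers no to 2 or 3 is expressly rejected, whatever the caregiver could do.

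Three related inconsistencies sit beside the routing.

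- Step 5 and the script's heading place the cognition screener before the questions; the acceptance rule places it after them.
- The heading assigns the script to Aim 2, whereas the randomised trial is Aim 1 in Section (1)(c).
- Section (5), Aim 1, Protection against Risk, limits access to the medication data to the Veteran and the study pharmacist, which does not fit a caregiver exchanging the list on the Veteran's behalf.

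**The case against.** The strongest reply is that this is a drafting slip. A script that on one reading admits nobody cannot have been meant literally, and trained staff would see the two intended routes. If the acceptance line is taken as two alternatives (yes to 3, or yes to 4 and 5), with the helper questions reserved for Veterans without a computer, both online self-managers and caregiver-assisted Veterans without a computer are admitted. That may well be the intention, but the text does not say so. It would also still leave out a Veteran with a computer who does not use the internet but has an online caregiver.

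The text has limits as a source. A figure is missing just above question 1, the bracket at question 5 is not closed, and the verbal-consent reference at question 4 may point to consent pages that are not reproduced. The question numbers and routing words are nevertheless intact, and the conflict lies in them.

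A reader might infer that 240 patients could not be recruited. The documents do not support that. They give no share of Veterans who have a helper, can use Secure Messaging, or have an online helper. At the CLC, about 10 discharges home a week over 50 weeks is 500, against 100 enrolments sought (100/500 = 20%), and the plan calls that estimate conservative. The West Roxbury pool is not given. A shortfall is possible but not shown.

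A reader might also infer bias in the treatment effect. Screening precedes randomisation and applies equally to both arms, so the comparison between them is not biased by it.

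**Conclusion.** The script is wrong as written. Its notes and closing rules contradict one another and do not match criteria a to d or the intervention text, and neither reading of the question order gives a workable rule. This rests on the wording alone and needs no assumed figures.

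The consequence is conditional. Literal use would narrow enrolment to online Veterans who also have an online helper (reading A) or stop it altogether (reading B); improvised use would make eligibility depend on the screener. The documents do not show which happens, so it would be too strong to say that the trial will enrol an unintended population. It would also be too strong to say that the caregiver route is closed to everyone: it is expressly closed to Veterans with a computer who answer no to 2 or 3, and left without a rule for those with no computer. What is at stake is who is enrolled, the reproducibility of screening and generalisability. The size of any loss cannot be computed from the documents.

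**What to change.** Replace the notes at questions 1, 4 and 5 and both closing rules with one either/or rule. A Veteran is eligible if he or she uses, or is willing to use, Secure Messaging (yes to 1, 2 and 3), or if an online helper will use it on the Veteran's behalf with the Veteran's agreement (yes to 4 and 5). In the same amendment:

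- state whether a Veteran who has a computer but answers no to 2 or 3 may use the caregiver route;
- reconcile the caregiver route with the limit on access to medication data in Section (5);
- record for each participant which route was used, so that the enrolled population can be described;
- relabel the script as Aim 1 and place the cognition screener once, consistently with steps 5 and 6.

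The cost is a one-paragraph script amendment, an aligned sentence on data access and brief retraining of screening staff. No extra patients or procedures are needed, and the sample size and analysis do not change.
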